4.2 Exclusion Criteria

Potential participants meeting any of the exclusion criteria at baseline will be excluded from participating in any part of the study. The exclusion criteria for this study include:

1. Not a registered Blued app user
2. < 18 years of age
3. Not male sex at birth
4. Does not report anal sex with a man in the last 6 months
5. Has previously tested positive for HIV
6. Not eligible for PrEP per published China guidance
7. Unable to complete study instruments in Mandarin Chinese
8. Not a resident of the metropolitan area of Beijing or Chengdu, China
9. Currently enrolled in another HIV prevention study
10. Evidence of fraudulent participation, such as a duplicate IP address, multiple screening attempts, duplicate emails, etc.

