5.3.2 Additional Blued+ Components

After the 3-month period, additional app components will be unlock in the health portal for each participant. These intervention components include:

Educational materials focused on PrEP as well as other sexual health topics. Topics of education may include an overview of PrEP and PrEP medication, the effectiveness of PrEP, PrEP payment, side effects, stigma, and where to access PrEP, among other topics related to prevention of HIV and STIs.

Additionally, participants will receive theory-based sexual health and prevention messages delivered via the Blued+. These messages will be developed with the goal of creating a comprehensive messaging package to improve participants' self-reported sexual health and prevention behaviors, beliefs, and attitudes. Participants will also receive a screener quiz that allows them to assess whether PrEP is right for them and encourage them and link to PrEP care. Those participants who do choose to initiate PrEP will receive the FTC/TDF, associated laboratory testing, and clinical care free of charge. Participants will be encouraged to schedule a visit with a study provider in each intervention city in-person or online, and will access PrEP free of charge through these study clinics.

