6.0 MEASURES

A summary table of study measures, and sources for each measure, are provided in the table below. Measurement of tenofovir-diphosphate (TFV-DP) levels will be conducted using liquid chromatography/tandem mass spectrometry methods on DBS samples. TFV-DP level can be translated to an interpretation that indicates mean number of days per week PrEP is ingested over a period of approximately one month. The cutpoint used will be TFV-DP levels considered a surrogate for substantial protection: >700 fmol/punch, a level indicating >4 doses/wk.

Construct	Measure	Data source	Definition	Analysis
PRIMARY OUTCOMES				
Feasibility	Home HIV test orders	Order fulfillment	Proportion of participants sent a home HIV test	Benchmark ≥ 30%
Feasibility	Condom orders	Order fulfillment	Proportion of participants sent 'choice' condom package	Benchmark ≥ 30%
Feasibility	PrEP initiation	Clinical site data	Proportion of participants receiving a PrEP prescription	Benchmark ≥ 20%
Acceptability	Systems Usability Scale ^{126, 127}	Survey	10-item scale, good score is >71	Benchmark: Good score (≥ 71 out of 100)
Acceptability	Ratings for intervention components ⁷²	Survey	Likert acceptability rating for each intervention component (e.g. home HIV test)	Benchmark: Acceptable ratings (≥ 3 out of 5)
PRELIMINARY EFFICACY ASSESSMENT				
HIV testing	HIV testing ^{44,128}	Survey	Change in median number HIV tests	GEE model
Condom use	Condom use ^{44,128}	Survey	Change in proportion of participants reporting always using condoms for anal sex	GEE model
PrEP Use	PrEP use ¹²³⁻¹²⁵	Laboratory data	Number participants with protective levels of TDF-DP	Descriptive report
THEORETICAL ASSESSMENT				
Prevention cascade	PrEP cascade levels ¹²⁹	Survey and clinical site data	PrEP awareness, willingness, prescription, persistence in care, and medication adherence	Descriptive and logistic regression
Theoretical assessment	Unified Theory of Acceptance and Use of Technology (UTAUT2) ¹²¹	Survey	Validated items for performance expectancy, effort expectancy, social influence, hedonic motivation, and habit.	Descriptive and GEE model to estimate SEM parameters
PROCESS OUTCOMES				
Process	New HIV testers	Survey	Proportion changing from never to ever HIV test	Descriptive report
Process	New condom users	Survey	Proportion changing from none to some condom use	Descriptive report
Process	Visits to local health clinics	Survey	Proportion receiving HIV services at health departments	Descriptive report

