10.3 Preliminary Efficacy Assessment

Preliminary efficacy assessments will describe differences in outcomes for the intervention, compared to the baseline period, for the median number of HIV tests and the proportion reporting all anal sex acts as condom-protected. A generalized estimating equations (GEE) repeated measures analysis will be conducted for the binary outcome of HIV testing (test/not testing). The GEE model will contain the seven time periods with primary comparisons of 0-month (first baseline) measurement to 6-month (end wash-out baseline period measurement and to 12-month (end first intervention period) measurement. Time will be considered as a fixed effect to compare proportion tested across intervals, with a random intercept for individuals. A similar GEE model will be conducted for the condom outcome (always/not always condom use). Logistic regression models will be fitted to understand PrEP cascade progressions, with the main analysis being any forward progress (yes/no) in the overall cascade between 0-month and 15-month measurements. These analyses will consider variables of progression in the PrEP cascade. Time at which cascade progress was made (e.g. 3 months) will be entered as a co-variate. A multifaceted approach to address missingness for our outcomes will be used. Primary analyses will treat values as missing at random. Sensitivity analyses will re-analyze data using both last-value-carried-forward and multiple imputation methods.

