10.4 Theoretical Assessments

Theoretical assessments will include descriptive and regression models to explore PrEP cascade level and constructs of the UTAUT2. We will add UTAUT2 constructs as independent variables to the above specified GEE models. Analyzing constructs of the UTAUT2 model will allow for estimation of structural equation modeling coefficients to inform assessment of required sample size to determine theoretical components of an eventual SEM in a future RCT of the intervention (Aim 4). Analysis will also inform our understanding of whether the theoretical model is appropriate for capturing pathways of the intervention effects. Process outcomes will be reported with descriptive statistics.

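### The any-forward-progress cascade analysis in Section 10.3 weights all steps equally, names no adjustment for starting level and gives no rule for men already at the top, so its results depend partly on the starting mix

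*Combined protocol and SAP*

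**What the plan says.** Section 10.3 (Preliminary Efficacy Assessment) fits logistic regression models to cascade progression, "with the main analysis being any forward progress (yes/no) in the overall cascade between 0-month and 15-month measurements". It adds two statements about the model's terms: "These analyses will consider variables of progression in the PrEP cascade", which is not explained further, and "Time at which cascade progress was made (e.g. 3 months) will be entered as a co-variate".

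The measures table in Section 6.0 defines the levels as "PrEP awareness, willingness, prescription, persistence in care, and medication adherence". With unawareness as the floor, that makes six possible states.

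Section 5.3.2 unlocks the following for every participant after month 3: "Educational materials focused on PrEP as well as other sexual health topics". Sections 4.1 and 4.2 do not exclude men already using PrEP. The nearest exclusion is "Currently enrolled in another HIV prevention study".

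Two other parts of the plan touch the cascade. Section 10.4 says: "Theoretical assessments will include descriptive and regression models to explore PrEP cascade level and constructs of the UTAUT2". Section 6.0 has a separate primary feasibility measure: "Proportion of participants receiving a PrEP prescription".

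**The concern.** Collapsing an ordered scale to one yes/no discards two pieces of information: which step was taken, and which steps were open to the man.

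- **Equal weight.** A man who becomes aware of PrEP after reading material given to everyone counts the same as a man who obtains a prescription.
- **No starting level.** The chance of moving up at least one step will probably differ by step. If it does, any characteristic associated with the month-0 level will appear to predict progress even when it affects no step. The time-of-progress term cannot stand in for starting level, since men who do not progress have no such time.
- **Ceiling.** A man at the top at month 0 cannot progress, yet nothing takes him out of the denominator.

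Section 10.2 says these additional analyses will inform the design of a later trial, and Aim 4 relies on that. A progress rate that shifts with the starting mix carries over poorly to a trial population that starts elsewhere. The problem would remain if the 0-to-15-month window and the time covariate were both revised.

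**Working it through.** The plan states no rate, effect size or precision for this outcome, so there is no figure to reproduce. The half-widths in Section 10.2 concern the benchmark proportions. **All inputs below are assumptions**, because the documents give neither a starting distribution nor step probabilities.

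**Formula.** Let π_k be the share starting at level k and s_k the probability of moving up at least one step. Expected progress is p = Σ π_k s_k.

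**1. Spurious odds ratio.** Five states are used, with persistence and adherence merged at the top: unaware / aware / willing / prescribed / top. Group A starts 40/30/25/3/2%, and group B 10/30/45/5/10%. Both have the same s_k: 0.90, 0.30, 0.15, 0.50, 0.

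- A: 0.40×0.90 + 0.30×0.30 + 0.25×0.15 + 0.03×0.50 = 0.5025
- B: 0.10×0.90 + 0.30×0.30 + 0.45×0.15 + 0.05×0.50 = 0.2725
- Odds ratio: (0.5025/0.4975) / (0.2725/0.7275) = 2.70

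Within each starting level the true odds ratio is 1 by construction, so adjusting for starting level removes the whole effect. Variations:

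| Change | A | B | Odds ratio |
|---|---|---|---|
| As above | 0.5025 | 0.2725 | 2.70 |
| s = 0.7, 0.3, 0.15, 0.5 | 0.4225 | 0.2525 | 2.17 |
| s = 0.5, 0.3, 0.2, 0.5 | 0.3550 | 0.2550 | 1.61 |
| s = 0.3 at every step below the top | 0.2940 | 0.2700 | 1.13 |
| First row, top-level men removed | 0.5025/0.98 = 0.5128 | 0.2725/0.90 = 0.3028 | 2.42 |
| First row, unaware men start as aware | 0.2625 | 0.2125 | 1.32 |

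In the 1.13 row the excess comes entirely from the ceiling: with top-level men removed, both groups are at 0.30. In the 2.70 row most of it comes from the assumed gap in awareness.

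**2. Share of outcome variance due to starting level.** R² = Σ π_k (s_k − p)² / [p(1 − p)]. Twenty scenarios combined:

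- four starting mixes (unaware/aware/willing 40/25/35, 10/20/70 and 20/30/50, plus 20/25/45 with 10% already on PrEP);
- five sets of probabilities for the first three steps (0.9/0.5/0.15, 0.9/0.5/0.2, 0.9/0.7/0.3, 0.6/0.4/0.2 and 0.3/0.3/0.3), with 0.7 for each later step.

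The largest case is 40/25/35 with 0.9/0.5/0.15. There p = 0.36 + 0.125 + 0.0525 = 0.5375 and Σ π_k s_k² = 0.3944, so R² = (0.3944 − 0.2889)/0.2486 = 0.42. The range over the twenty is 0 to 0.42. For the groups in step 1, R² is 0.45 in A, 0.28 in B and 0.41 pooled equally.

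**3. Progress without a prescription.** In the 0.42 case, new prescriptions are 0.40×0.9×0.5×0.15 + 0.25×0.5×0.15 + 0.35×0.15 = 0.098. So 1 − 0.098/0.5375 = 82% of progressors have none. The range over the twenty is 23% to 82%.

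**4. Same prescription uptake, different starting mix.** Fix new prescriptions at 20% of all men, keep 0.9 and 0.5 for the first two steps, and solve for the willing-to-prescribed probability.

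- Mix 10/20/70: 0.20/0.845 = 0.237, so p = 0.09 + 0.10 + 0.70×0.237 = 0.356
- Mix 40/25/35: 0.20/0.655 = 0.305, so p = 0.36 + 0.125 + 0.35×0.305 = 0.592

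Any-progress differs by about 24 points at equal prescription uptake. The share of progressors without a prescription is 44% and 66% respectively.

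**The case against.** The strongest reply has five parts.

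- **Uptake is judged elsewhere.** PrEP prescription is a primary outcome with its own benchmark, and Section 10.4 also explores cascade level. A high any-progress rate with few prescriptions would therefore be visible. This stands and limits the harm. It does not repair the model: the benchmark is a proportion, not an analysis of who progresses, and Section 10.4 names no adjustment for starting level either.
- **Starting level may be covered.** The undefined variables of progression could include it. That is possible, so the plan cannot be said to rule adjustment out, but it does not specify it. Equally, Section 10.3 names no personal characteristics as predictors, so which odds ratios would be affected is open.
- **Few men may start unaware.** Under Section 5.1.2, consent and a comprehension quiz precede the baseline survey, and Section 11.2 says the electronic consent covers all procedures. Many men could be aware by the time month 0 is measured, depending on how the survey asks. This stands as a caution on size: it takes the example from 2.70 to 1.32.
- **Few men may start at the top.** Section 1.0 says PrEP was not approved in China. Section 5.4.4 nevertheless describes locally available approved FTC/TDF tablets, so the number need not be zero. The ceiling is probably the smaller part.
- **Non-primary analysis, non-powered pilot.** Correct, and no decision rule depends on it.

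A reader might infer that the outcome mostly measures starting level. The documents give no figures to support that, and starting level explained less than half of the outcome variance in every scenario tried.

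**Conclusion.** The point holds in a limited form. Section 10.3 as written counts every step equally, names no adjustment for month-0 level and gives no rule for men who cannot progress. The progress rate and any odds ratios then depend partly on the starting mix.

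The size is unknown. The illustrative spurious odds ratio of about 1.1 to 2.7 rests entirely on assumed starting mixes and step probabilities. The upper end needs a large gap in baseline awareness between groups and should not be read as an estimate for this study. If every step were equally likely and nobody started at the top, there would be no distortion of the odds ratio, though steps would still be counted equally. The consequence is confined to a secondary analysis in a pilot that is not powered for effects.

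**What to change.** In Section 10.3:

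1. Add month-0 cascade level as a categorical covariate, with upper levels collapsed where sparse. A starting group of 2% to 3% of 400 is only 8 to 12 men.
2. Restrict the risk set to men below the top level at month 0, and say how men already on PrEP at month 0 are classified. Section 8.1 collects dried blood spots only from men who initiate PrEP, at an interim visit, so no laboratory adherence measure at month 0 is described. This is a further reason to collapse the upper levels.
3. Report progress by starting level, including new prescriptions among men not yet prescribed at month 0, beside the any-progress figure.

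A step-specific or ordinal model of the month-15 level is optional and a matter of preference.

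Cost: wording only. Month-0 level is already needed to score progress, so no new data are required. The model gains a few terms, and its denominator falls by the number of men at the top. This is a free improvement.

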Study Design:

The pilot study will be an interrupted time series cohort of 400 MSM. In two cities, a three-month baseline standard of care (SOC) period with measurement at 0 and 3 months will be followed by a 12-month intervention period with the measurement at 6, 9, 12, and 15 months. The longitudinal design will allow for 1) assessment of feasibility and acceptability outcomes, 2) development of the logistical and operational needs to provide the app-based intervention, and 3) development of estimates for key parameters to design a future, definitive study to determine intervention efficacy.

Standard of care will consist of the existing Blued app and local health services. Blued app access currently includes health education components such as information regarding HIV testing and pre-recorded health messages from Chinese celebrities. Participants will have access to in-person no-cost services for HIV testing and condom pick-up from local non-governmental organizations (NGOs) that support MSM in both cities.

At three months, participants will be provided with educational materials in the health portal as well as theory-based HIV prevention messages, along with home HIV test kits and condoms. This intervention will have a health portal that houses all HIV prevention functionalities. The exact nature of the interventions included will be further defined by the qualitative work, as additional services may be identified as essential to an HIV prevention package in China. These may include services such as peer support or stigma reduction. Additionally, participants will receive PrEP medication, laboratory, and care costs free of charge.

In the portal, users will be able to explore health-supporting functions of the app and access offline services, including behavioral risk assessments, an HIV prevention platform, HIV testing, linkage to care for those testing positive for HIV, in-app screening and referral to HIV pre-exposure prophylaxis (PrEP) and sexually transmitted infection (STI) services, and provision of PrEP with emtricitabine/tenofovir disoproxil fumarate (FTC/TDF).

Study Population:

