10.2 Power to Detect Effects in Primary Outcome

This is a feasibility pilot and therefore is not powered to detect significant differences relative to the baseline period. The use of a non-powered pilot design is called for by the MP3 mechanism. A sample of 200 individuals per intervention city was selected based on what was determined to be achievable given budget and time constraints. It is also anticipated that this number will provide estimates of key parameters with sufficient precision. For instance, the prevalence of our binary benchmarks (home HIV

test orders, PrEP initiation) would be estimable with the following 95% confidence intervals half-width at specified prevalences: $20\% \pm 4\%$; $30\% \pm 5\%$; $50\% \pm 5\%$.

Led by the study statistician, additional analyses will be conducted to assess (1) preliminary efficacy with endpoints measuring change from baseline to intervention periods in HIV testing, condom use, and PrEP use, (2) theoretical efficacy with endpoints in the PrEP cascade and UTAUT2 constructs, and (3) process outcomes with endpoints of new HIV testers, new condom users, and app use metrics. These assessment will leverage the pilot's interrupted time series design and inform future clinical trial design.

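### The main PrEP-cascade logistic model takes as a covariate the time of progress, which exists only for men whose outcome is yes, so the model as written gives no valid estimate

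*Combined protocol and SAP*

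**What the plan says.** Section 10.3 (Preliminary Efficacy Assessment) introduces the cascade analysis as follows: "Logistic regression models will be fitted to understand PrEP cascade progressions". It names the "main analysis being any forward progress (yes/no) in the overall cascade between 0-month and 15-month measurements", which is one binary value per participant over the whole study. After a sentence on considering progression variables comes the rule at issue: "Time at which cascade progress was made (e.g. 3 months) will be entered as a co-variate".

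The measures table in section 6.0 lists five cascade levels (awareness, willingness, prescription, persistence in care, adherence) and gives the analysis only as "Descriptive and logistic regression". The missing-data text in 10.3 opens with "A multifaceted approach to address missingness for our outcomes will be used". It is about outcomes: missing at random in the primary analyses, with last value carried forward and multiple imputation as sensitivity analyses.

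Section 10.2 lists "theoretical efficacy with endpoints in the PrEP cascade and UTAUT2 constructs" among the additional analyses and says these will inform the design of a future trial. The Schema (Study Design) describes a "three-month baseline standard of care (SOC) period with measurement at 0 and 3 months", followed by 12 months of intervention with surveys at 6, 9, 12 and 15 months.

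**The concern.** The outcome decides whether the covariate exists. A man who progressed has a time of progress. A man who did not has none, and no amount of follow-up would supply one. A logistic model needs a covariate value for every man in both outcome groups, so someone must drop the non-progressors or invent a value for them. The plan chooses neither.

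This is the named main analysis of the PrEP cascade, and it is meant to feed the design of the definitive study. As written it leads either to a fit that fails or to a time effect produced by the analyst's coding, which can carry a very small p-value and be taken for a finding.

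**Working it through.** The plan states no figure for this model, so there is none to reproduce.

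**Inputs from the documents.** n = 400 (sections 3.0 and 3.2). The outcome is any forward progress over months 0 to 15 (10.3). The possible times of progress are the later survey months 3, 6, 9, 12 and 15 (Schema; 11.5).

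**Assumptions.** The documents give neither the share who progress nor its timing. I use shares of 10%, 25%, 40% and 60%, so n1 = 40, 100, 160 or 240 progressors and n0 = 400 − n1. Progress is spread evenly over the five months, so the progressors' mean time is (3+6+9+12+15)/5 = 9 months. Let c be the code given to non-progressors.

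**Step 1: complete cases.** Only the n1 progressors have a time. Every outcome is yes and there is nothing to model.

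**Step 2: a code at or beyond the edge of the observed times.**
- c = 0 or c = 18: all progressors lie strictly on one side of all non-progressors. This is complete separation, and no finite maximum-likelihood estimate exists.
- c = 15, the end of follow-up: the groups overlap only at month 15. This is quasi-complete separation, and the time coefficient runs to minus infinity. c = 3 is the mirror case.

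These results need no assumption about the share. They held in all 16 combinations of the four shares with four timing profiles (even, early, late, peak at month 6). Simulated fits at 20%, 30% and 50% progress with one baseline covariate agreed. With c = 15 the time coefficient was about −7 to −8, its standard error about 780 to 7,200, and the fit did not converge.

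**Step 3: an interior code.** The score for the time coefficient, evaluated at zero, is

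U = n1 × (n0/n) × (mean time of progressors − c).

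The log-likelihood is concave, so the fitted coefficient has the sign of (9 − c). For the 25% share, U = 100 × (300/400) × (9 − c), which is +225 at c = 6, 0 at c = 9 and −225 at c = 12. The fitted odds ratios per 3 months of time are:

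| Code c | 10% | 25% | 40% | 60% |
|---|---|---|---|---|
| 6 | 9.2 | 4.9 | 3.5 | 2.5 |
| 9 | 1.00 | 1.00 | 1.00 | 1.00 |
| 12 | 0.11 | 0.20 | 0.29 | 0.39 |

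Every p-value at codes 6 and 12 is below 1e-8. Within each column the men and their outcomes are the same, and only the code changes.

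**Step 4: imputing times from the progressors.** The model converges, but the time coefficient is about zero by construction (0.008, −0.011 and −0.030 at simulated shares of 20%, 30% and 50%). It describes a quantity that non-progressors do not have.

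**Step 5: do the alternatives work?** With the time term dropped, the same simulated data converge at all three shares. The baseline covariate's log odds ratio is 0.49 (SE 0.15), 0.32 (SE 0.10) and 0.44 (SE 0.11).

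For a person-interval model, assume an equal quarterly probability h = 1 − (1 − share)^(1/5) and no dropout. The number of rows is 400 × share / h.
- 10% share: h = 0.0209 before rounding to four places; about 1,918 rows and 40 events.
- 60% share: h = 0.1674; about 1,433 rows and 240 events.

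The log odds ratio for later quarters against months 0 to 3 has a standard error of 0.39 at the 10% share, falling to 0.16 at 60%. Both alternatives are estimable.

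**The case against.** The strongest reply is that 10.3 speaks of logistic models in the plural, and the time sentence may be meant for only some of them. In a step-specific model, such as persistence among men already prescribed PrEP, the time of the earlier step is defined for every man analysed and is a sensible covariate. The example of 3 months would also fit a survey-wave term in a person-interval model. Either version can be estimated.

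That shows how the sentence could be made to work, but the plan does not say it. The time sentence follows the naming of the main analysis without excluding it. Nowhere does the plan state a person-interval layout, a restriction to progressors or a step-specific model. The same section does set out a repeated-measures time structure for HIV testing and condom use.

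Three narrower points stand in part. Nothing in the documents suggests coding non-progressors at 6, 9 or 12 months, so the odds ratios illustrate sensitivity to coding and do not predict what the team will do. The more natural codes usually show up as a failed or unstable fit. The failure also belongs to the model with this term, since without it the yes/no model is sound. Finally, the pilot is explicitly unpowered and no stated design decision rests on this coefficient, which limits the harm without repairing the rule.

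**Conclusion.** The concern holds. Read as written, the main cascade model conditions on a covariate whose existence is determined by the outcome. It yields no fit, a separated fit, or an estimate fixed by an unstated coding choice. The separation results are structural and hold for any share of men who progress. Only the odds ratios, 9.2 down to 2.5 at one code and 0.11 up to 0.39 at another, rest on the assumed shares and even timing.

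The point should be fixed before analysis. Its reach is limited to a secondary analysis: the benchmarks in 10.1 and the descriptive cascade report are not touched.

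**What to change.** Amend 10.3 in one of two ways.

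- Keep the yes/no model, remove time of progress, and name baseline covariates only, including the cascade level at month 0.
- If timing is of interest, state a discrete-time logistic model. Use one row per man per survey interval until first forward progress, restricted to men still able to progress. The outcome is forward progress in that interval, and the covariates are survey interval as the time term plus the same baseline covariates.

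If a step-specific model was intended for the time covariate, say which step it models and which men enter it.

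A useful addition, separate from curing the defect, is to report progress in months 0 to 3 apart from months 3 to 15, because the first interval is standard of care. The plan does not itself credit the whole 0 to 15 month total to Blued+.

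The cost is a few sentences and slightly more programming. Survey and clinic data already planned are enough.

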3.2 Sample Size

Over the entire study period, 400 participants will be enrolled in the prospective pilot study intervention. All participants will be followed longitudinally for 15 months.

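### Neither planned missing-data sensitivity analysis is a controlled check on the missing-at-random assumption; delta-adjusted multiple imputation would be a cheap improvement

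*Combined protocol and SAP*

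**What the plan says.** The missing-data plan is the end of Section 10.3. It sets the base assumption, "Primary analyses will treat values as missing at random", and then adds: "Sensitivity analyses will re-analyze data using both last-value-carried-forward and multiple imputation methods". It gives no imputation model, expected dropout, delta, tipping point or other missing-not-at-random scenario, and no other section supplies one.

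The analyses concerned are two repeated-measures GEE models for binary outcomes: tested or not, and always or not always using condoms. On their structure the plan says: "Time will be considered as a fixed effect to compare proportion tested across intervals, with a random intercept for individuals". Both outcomes come from the surveys (Section 6.0, where the testing measure is "Change in median number HIV tests"), so a missed survey is a missing outcome.

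The Study Design part of the Schema puts months 0 and 3 under standard of care, "followed by a 12-month intervention period with the measurement at 6, 9, 12, and 15 months". Section 10.3 names the comparisons of month 0 with months 6 and 12 as the main ones. Its label for month 6 does not match the Schema; this note follows the Schema.

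**The concern.** A sensitivity analysis for missing data should show how far the result moves when the untestable assumption is relaxed by a known amount. Here the plausible threat is that men who disengage from the app also stop answering surveys and go back to their earlier testing habits. Recruitment, consent and surveys are all remote, and the app is the intervention, so the two forms of disengagement could well go together.

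Imputation under MAR fills in such men as if they behaved like similar men who stayed. Carry-forward fills them in with whatever they last reported. Having tested in one interval is not a lasting state, so the carried value can record tests that never happened or miss tests that did. Always using condoms is a behaviour over a period rather than an event, but freezing it has a similar effect if behaviour changes.

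What is at stake is the estimated change from baseline. Section 10.2 says these analyses will inform future trial design, and Aim 4 relies on the pilot for that purpose. An inflated change would make the later trial too small.

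**Working it through.** The plan states no figure on this point, so there is none to reproduce. The rates below are assumptions chosen for illustration.

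**Assumed inputs.** Proportion tested per interval: 17% under standard of care and 35% under the intervention, a difference of 18 points. Everyone answers at month 0. At each later survey 5% (or 8%) of those remaining are lost for good, independently of outcome. The survey times are from the Schema.

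**Step 1: proportion lost.**
- Before giving any intervention-period answer (lost at the month 3 or 6 survey): 1 − 0.95² = 0.0975; 1 − 0.92² = 0.1536.
- By month 12 (four surveys): 1 − 0.95⁴ = 0.1855; 1 − 0.92⁴ = 0.2836.

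**Step 2: carry-forward under purely random loss.** Men lost before month 6 carry 17%; men lost later carry 35%. From month 6 to month 15 the carried-forward proportion is therefore 35 − 18 × (proportion lost before an intervention answer):
- 5% loss: 35 − 18 × 0.0975 = 33.2%.
- 8% loss: 35 − 18 × 0.1536 = 32.2%.

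The truth is 35%, so carry-forward is 1.8 to 2.8 points low although MAR holds.

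**Step 3: lost men revert to 17%.** Observed answers are the same as in Step 2, so each analysis gives the same result as before. The truth at month 12 changes:

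| Loss per survey | Truth if lost men revert | MAR estimate | MAR error | Carry-forward |
|---|---|---|---|---|
| 5% | 35 − 18 × 0.1855 = 31.7% | 35% | +3.3 | 33.2% |
| 8% | 35 − 18 × 0.2836 = 29.9% | 35% | +5.1 | 32.2% |

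Simulation of the same set-up with a random intercept agrees to about 0.1 point. As a range over total loss with full reversion, the MAR error is 18 × 0.10 = 1.8, 18 × 0.20 = 3.6 and 18 × 0.30 = 5.4 points.

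**Step 4: a separate simulation.** It used 1,000,000 men, six quarterly binary outcomes, a logistic random intercept with SD 1.2, testing rising from about 26% to 50%, and 22-25% missing at month 12. Loss per survey was 6% when random. Otherwise it was 3% for men who tested and 9% for men who did not, judged on the previous outcome (MAR) or the current unseen one (not at random). Errors at month 12, in points:

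| Loss mechanism | Available cases | Multiple imputation | Carry-forward |
|---|---|---|---|
| Completely random | +0.1 | +0.1 | −3.6 |
| MAR | +1.3 | 0.0 | −7.9 |
| Not at random | +2.6 | +2.1 | −2.9 |

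When MAR fails, imputation stays close to the available-case result, and both err the same way. When MAR holds, carry-forward shows its largest gap. So agreement with the first is not evidence for MAR, and a gap from the second is not evidence against it. With a flat outcome and completely random loss, the carry-forward error was 0.0.

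**The case against.** Several counter-arguments have force.

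*Multiple imputation is not a mere repeat of the primary analysis.* This stands. Unweighted GEE is not generally valid under MAR, whatever the plan calls it, and Step 4 shows imputation removing a 1.3-point error. Section 10.3 also combines GEE with a random intercept, so it is unclear which model is meant. A reader might infer that the imputation analysis is worthless; the plan does not support that. It is useful, but it does not probe MAR.

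*Carry-forward does leave MAR in the feared direction.* This also stands. Under reversion it matches the truth at month 6 (33.2% and 32.2% in Step 3's set-up), one of the two main comparisons, and lies nearer the truth than the MAR estimate at month 12. A reader might infer that it reveals nothing about disengagement; that is too strong. The defect is that the size of the departure is set by when men happen to leave, and the same figure appears whether or not they revert.

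*No analysis of the observed data can settle whether MAR holds.* True, and it applies to the remedy as well. Delta adjustment does not detect the mechanism; it shows the consequence of a departure that is stated in advance.

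*Little depends on it.* Section 10.3 describes differences in an unpowered pilot, Section 10.1 makes the benchmarks primary, and no decision threshold is attached to these estimates. That limits the weight of the point. It is also true that errors of 3 to 5 points are no larger than the roughly 5-point half-widths in Section 10.2, but a systematic error is not covered by a confidence interval.

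**Conclusion.** The point holds as a cheap improvement. Section 10.3 offers no controlled departure from MAR: one sensitivity analysis keeps the assumption, and the other abandons it by an uncontrolled amount and is biased under random loss whenever the outcome changes.

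On the assumed rates, carry-forward is 1.8-2.8 points low under random loss, and the MAR estimate at month 12 is 3.3-5.1 points high if lost men revert fully. These sizes depend on the 17% and 35%, the 5-8% loss and full reversion, none of which is in the documents. The survey recall window is also not stated.

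Two stronger conclusions might be drawn and are not supported. First, the sign of the change is not in doubt on these rates: even counting every missing man as untested gives 35 × 0.8145 = 28.5% or 35 × 0.7164 = 25.1% at month 12, against 17% at baseline. The size of the change is what is uncertain. Second, this does not undermine the feasibility and acceptability benchmarks, which are a separate primary analysis; the uptake benchmarks rest on order and clinic records.

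**What to change.** In Section 10.3, keep multiple imputation under MAR as the base and state its imputation model. Replace carry-forward with delta-adjusted multiple imputation for HIV testing and for condom use. Shift imputed intervention-period values toward the man's own standard-of-care level over a range fixed in advance, for example from no shift (MAR) to full reversion and somewhat beyond.

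Report the change from month 0 to months 6 and 12 across that range. Include the shift at which the estimated change, or its confidence limit, reaches zero, or say that no shift in the range does so. This gives the tipping point a defined target, since the plan sets no threshold of its own.

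Counting missing surveys as not tested or not protected may be added only if labelled a worst-case bound. Under purely random loss it gives about 27% (35 × 0.95⁵) or 23% (35 × 0.92⁵) at month 15 against a true 35%, further off than carry-forward.

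The cost is a sentence or two of text and a little more programming. No new data are needed. The sensitivity results may look less favourable.
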